
Primary
 
Safety: To determine the safety and reactogenicity of the hAd5-S-Fusion+N-ETSD vaccine at two dose levels for subcutaneous administration, and for sublingual and intranasal dosing.
 
Immunogenicity: To determine immunogenicity of hAd5-S-Fusion+N-ETSD as determined by changes in humoral response.
	
Safety:
 
 • Incidence of MAAEs and SAEs through 1 week post final vaccine administration • Incidence and severity of solicited local reactogenicity AEs through 1 week post final vaccine administration • Incidence and severity of solicited systemic reactogenicity AEs through 1 week post final vaccine administration • Incidence and severity of unsolicited AEs through 1 week post final vaccine administration • Incidence of MAAEs and SAEs through 30 days and 6 months post final vaccine administration • Incidence and severity of unsolicited AEs through 30 days and 6 months post final vaccine administration • Incidence of abnormal changes of laboratory safety examinations • Changes in vital signs 
Immunogenicity: Timing per Schedule of Events
 
 • GMFR in IgG titer to SARS-CoV-2 S, RBD and N. • GMT of S-specific, RBD-specific, and N-specific antibodies against 2019 novel coronavirus tested by ELISA in serum . • Percentage of participants who seroconverted (defined as 4-fold change in antibody titer relative to baseline) . • GMFR in neutralizing antibody .

	
 • GMT of neutralizing antibody . • Seroconversion rate of neutralizing antibody (defined as 4-fold change in antibody titer relative to baseline) .
Secondary	
Safety: 
 • Ascertainment of HIV infections in vaccine recipients through 12 months post final vaccine administration 	Safety: 
 • New HIV infections in vaccine recipients by either two locally approved rapid antibody tests or by ELISA, conducted per Schedule of Events through 12 months post final vaccine administration
Exploratory	

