Immunogenicity: To determine cellular and mucosal immunogenicity of hAd5-S-Fusion+N-ETSD. To assess for any induction or enhancement of Ad5 immune response by the Ad5 vector in hAd5-S-Fusion+N-ETSD.	Immunogenicity: Timing per Schedule of Events 
 • T cell activity against SARS-CoV-2 S, RBD and N protein • Mucosal Immunogenicity as assessed by GMT of IgA antibody levels to SARS CoV-2 S protein, RBD and N protein • T cell activity and IgG titres against Ad5, comparing baseline to day 29 and day 181 and 202(in cohorts 3, 4, 5, 6 and cohorts 1 and 2 respectively)

Study Design:

This is a phase 1b, open-label study in adult healthy participants. This clinical trial is designed to assess the safety, reactogenicity, and immunogenicity of the hAd5-S-Fusion+N-ETSD vaccine and select a dose for future studies. The hAd5-S-Fusion+N-ETSD vaccine is a hAd5 [E1-, E2b-, E3-] vector-based targeting vaccine encoding the SARS-CoV-2 S and N proteins. The hAd5-S-Fusion+N-ETSD vaccine is designed to induce both humoral and cellular responses even in individuals with pre-existing adenoviral immunity. Thus, the potential exists for the hAd5-S-Fusion+N-ETSD to induce SARS-CoV-2 immunity and prevent or lessen the health impact of COVID-19 infection in healthy participants. Up to 60 healthy participants will be divided into 6 cohorts:

Study Cohorts, Dosing Schedules, Mode of Administration and Dose of hAd5-S-Fusion+N-ETSD

Cohort	Number of participants	Dosing Schedule	Mode of Administration	Dose
1	10	Day 1	SC	5×10^{10} VP
		Day 22	SC	5×10^{10} VP
2	10	Day 1	SC	1×10^{11} VP*
		Day 22	SC	1×10^{11} VP*
3	10	Day 1	SC	1×10^{11} VP*
4	10	Day 1	SL	1×10^{11} VP
5	10	Day 1	SC	1×10^{11} VP*
			and SL	1×10^{11} VP
6	10	Day 1	IN	2×10^{10} VP into each nostril**

SC= subcutaneous; SL= sublingual; IN= intranasal; VP= viral particles; * In the event of safety concerns participants will be dosed at 5×10^{10} VP/dose; ** Total IN dose is given is 4×10^{10} VP as vaccine will be administered into both nostrils

Cohort 1-2 enrolled participants who were SARS-CoV-2 antibody serology negative. For cohorts 3-6, only participants who are SARS-CoV-2 antibody serology positive will be enrolled to evaluate boosting of pre-existing SARS-CoV-2 immune responses and compare the effect of route of administration on the efficacy (and magnitude thereof), reactogenicity and safety of the boosting effect.

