The Safety Review Committee (SRC), including at least one qualified infectious disease physician independent of the Sponsor and trial reviews safety data.

The SRC will first assess safety when all Cohort 1 participants have completed the toxicity assessment period (defined as 7 days after first vaccine dose, i.e. study day 8). In the absence of safety concerns, enrolment in Cohort 2 will be initiated. The SRC will similarly also assess safety when each of Cohort 2, 3, 4 and 5 participants have completed the toxicity assessment period (defined as 7 days after first vaccine dose, i.e. study day 8). In the absence of safety concerns, enrolment in Cohort 3, 4, 5 and 6 respectively will proceed. Cohorts 3 and 5 will be dosed at 1×10^{11} VP/dose for SC administrations. If safety concerns are identified at the higher dose of 1×10^{11} VP/dose, Cohort 3 and 5 participants will be dosed at 5×10^{10} VP/dose for SC administrations.

All participants will have follow up study visits for the collection of safety, reactogenicity, and/or immunogenicity data at 7 and 14 days after each vaccine dose, 30 days after the last dose, and at 90, 180 and 365 days following the last dose. Additional follow up for safety information will occur via telephone contact as noted in the Schedule of Events.

Safety will be assessed for all participants and will include monitoring of vital signs, and incidence and severity of AEs. Blood samples will be collected for haematology and chemistry analyses and urine samples will be collected for urinalysis. Toxicities will be graded using the Guidance for Industry: Toxicity Grading Scale for Healthy Adult and Adolescent Volunteers Enrolled in Preventive Vaccine Clinical Trials (2007). Solicited local and systemic AEs and unsolicited AEs will be collected using diary cards for 7 days following any dose of vaccine.

Solicited local AEs to be assessed include

Subcutaneous dosing includes injection site:

- Pain,
- Itching,
- Induration,
- Swelling,
- Erythema.

Sublingual dosing include:

- Oral burning,
- Oral swelling,
- Difficulty swallowing,
- Difficulty breathing.

Intranasal dosing include:

- Nasal congestion and coryza
- Epistaxis,
- Pain in the nose,

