
11. HIV positive or other acquired or hereditary immunodeficiency.
 
12. Serious cardiovascular diseases, such as arrhythmia, conduction block, previous myocardial infarction, uncontrolled severe hypertension
 
13. History of hereditary, idiopathic or acquired angioedema.
 
14. Urticaria 12 months prior to screening.
 
15. No spleen or functional asplenia.
 
16. Platelet disorder or other bleeding disorder that may cause injection contraindication.
 
17. Chronic use (more than 14 continuous days) of any medications that may be associated with impaired immune responsiveness including, but not limited to, systemic corticosteroids exceeding 10 mg/day of prednisone equivalent, allergy injections, immunoglobulin, interferon, or immunomodulators. The use of low dose topical, ophthalmic, inhaled and intranasal steroid preparations will be permitted.
 
18. Prior administration of blood products within 120 days before first study vaccination.
 
19. Prior administration of other research medicines or investigational product within 30 days before first study vaccination.
 
20. Prior administration of attenuated vaccine within 30 days before first study vaccination.
 
21. Prior administration of inactivated vaccine within 14 days before first study vaccination.
 
22. Prior administration of SARS-CoV-2 vaccine or likely to receive SARS-CoV-2 vaccination within the upcoming 28 days
 
23. Current treatment with investigational agents for prophylaxis of COVID-19.
 
24. Have a household contact that has been diagnosed with COVID-19 within 14 days before first study vaccination.
 
25. Current anti-tuberculosis prophylaxis or therapy.
 
26. Currently receiving treatment for cancer or history of cancer in the last five years (except basal cell carcinoma of the skin and cervical carcinoma in situ).
 
27. According to the judgement of the investigator any medical, psychiatric, psychological, social, occupational or other conditions that could affect the participants ability to sign informed consent, provide safety assessment data or comply with the requirements of the study protocol.
 
28. Assessed by the Investigator to be unable or unwilling to comply with the requirements of the protocol.
	
Duration of Treatment: Each participant will receive hAd5-S-Fusion+N-ETSD on Day 1. Cohorts 1 & 2 receive a second dose of hAd5-S-Fusion+N-ETSD at Day 22.

--	--

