
Evaluation of Endpoints:
 
Safety: Safety endpoints include assessments of treatment-emergent MAAEs, SAEs, solicited local and systemic reactogenicity AEs, unsolicited AEs, safety laboratory tests, HIV testing and vital signs. Toxicities will be graded using the Guidance for Industry: Toxicity Grading Scale for Healthy Adult and Adolescent Volunteers Enrolled in Preventive Vaccine Clinical Trials (2007).
 
Immunogenicity: GMT of S-specific and N specific antibodies against 2019 novel coronavirus, GMT of neutralizing antibody, and GMT of IgA antibody levels will be evaluated. T cell activity against SARS-CoV-2 S, RBD and N protein will be measured by standard immune assays. Humoral and cellular immunity against the Ad5 vector will be measured at baseline, day 29 and day 181 and 202 (in cohorts 3, 4, 5, 6 and cohorts 1 and 2 respectively) to assess for any induction or enhancement of Ad5 immune responses.
	
Statistical Methods:
 
The purpose of this study is to determine the safety, reactogenicity, and immunogenicity of hAd5-S-Fusion+N-ETSD and select an optimal dose and formulation for future studies. Descriptive statistics will be presented for all study endpoints by individual cohort, pooled by dose level, and for all cohorts combined.
 
Safety will be assessed by the incidence of treatment-emergent MAAEs, SAEs, and solicited local and systemic reactogenicity AEs, and unsolicited AEs for the time period of interest, overall and by grade using the Guidance for Industry: Toxicity Grading Scale for Healthy Adult and Adolescent Volunteers Enrolled in Preventive Vaccine Clinical Trials (2007). Clinically significant changes in safety laboratory tests and vital signs also will be summarized. As suggested by the Ad5 literature and expert opinion, participants will be monitored for incident HIV infection during the follow up period .
 
Immunology analyses will be used to provide an assessment of immune responses. GMFRs and GMTs and their associated 95% confidence intervals (CIs) will be computed by exponentiation of the corresponding log-transformed means and 95% CIs. The percentage of participants who seroconverted (as defined as 4-fold change in antibody titer relative to baseline) and 95% Clopper-Pearson CI will be summarized. Neutralizing antibody levels and CD8+ and CD4+ T-Cell activity also will be summarized.

Figure 1: Study Schema

* In the event of safety concerns participants will be dosed at 5×10^{10} VP/dose

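### The dose-level summary compares seronegative two-dose participants at 5×10^10 VP with a mix of seronegative two-dose and seropositive one-day participants at 1×10^11 VP

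*Combined protocol and SAP*

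**What the plan says.** The Statistical Methods section of the synopsis gives as a purpose of the study to "select an optimal dose and formulation for future studies". It then states: "Descriptive statistics will be presented for all study endpoints by individual cohort, pooled by dose level, and for all cohorts combined". The supplied text does not restrict the dose pooling to one serostatus, schedule or route.

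The pools follow from the rest of the synopsis:

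- Study Design: "Up to 60 healthy participants will be divided into 6 cohorts", with 10 in each row of the cohort table.
- Serostatus: "Cohort 1-2 enrolled participants who were SARS-CoV-2 antibody serology negative". For Cohorts 3 to 6, "only participants who are SARS-CoV-2 antibody serology positive will be enrolled to evaluate boosting of pre-existing SARS-CoV-2 immune responses".
- Schedule (Duration of Treatment): "Cohorts 1 & 2 receive a second dose of hAd5-S-Fusion+N-ETSD at Day 22". Cohorts 3 to 6 are dosed on Day 1 only.
- Dose: Cohort 1 receives 5×10^10 VP and Cohort 2 receives 1×10^11 VP, both subcutaneously. "Cohorts 3 and 5 will be dosed at 1×10^{11} VP/dose for SC administrations". Cohort 4 receives 1×10^11 VP sublingually, and Cohort 5 receives that sublingual dose as well as its injection. Cohort 6 receives 4×10^10 VP in total intranasally.
- Fallback: the cohort table footnote allows 5×10^10 VP after safety concerns in Cohorts 2, 3 and 5. The Study Design text names Cohorts 3 and 5.

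The safety windows are tied to the last dose, for example "Incidence and severity of unsolicited AEs through 1 week post final vaccine administration". Diary cards cover the 7 days after each dose.

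**The concern.** A table with one column per dose level invites the reader to attribute column differences to dose. Here the columns also differ in who was vaccinated and how often.

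The immunogenicity endpoints do not mean the same thing across the pool. Titres, fold rises and the 4-fold seroconversion rule describe priming in Cohorts 1 and 2 and boosting of an existing response in Cohorts 3 to 6.

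The per-participant safety endpoints also differ. The window ending one week after the final dose runs to Day 29 (22 + 7) and covers two doses in Cohorts 1 and 2. In Cohorts 3 to 6 it runs to Day 8 (1 + 7) and covers one dosing day. Solicited local events are route-specific, so adding sublingual Cohort 4 to the high-dose pool dilutes the injection-site incidence.

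Choosing a dose is a stated purpose, and the text gives no rule that points the reader to the valid contrast. The pooled column also has 20 to 40 participants against 10 per cohort, which gives it a weight it has not earned.

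**Working it through.** **The plan's own figure.** 6 cohorts × 10 = 60, which matches the planned enrolment. The supplied text gives no power or sample-size calculation to reproduce.

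**Composition (no assumptions about outcomes).** The low-dose pool as planned is Cohort 1: 10/10 seronegative and two-dose. Dose level is not defined for Cohort 5 (two administrations of 1×10^11 VP) or across routes, so each reading of the high-dose pool is shown. Let s be its seronegative two-dose share.

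**Formulas, with no true dose effect.** Outcome values are assumed, because the documents give none.

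- GMFR: low/high = (seronegative GMFR ÷ seropositive GMFR)^(1−s). Assumed 20 and 3.
- GMT: high/low = (seropositive GMT ÷ seronegative GMT)^(1−s). Assumed 10,000 and 1,000.
- Any adverse event, risk p per dosing day, independent across doses and equal across routes: low = 1−(1−p)², high = s[1−(1−p)²] + (1−s)p, so the gap is (1−s)p(1−p). Assumed p = 50%.

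| Cohorts at 1×10^11 VP | n | s | GMFR (low dose 20) | GMT (low dose 1,000) | Any AE (low dose 75%) |
|---|---|---|---|---|---|
| 2+3 | 20 | 10/20 = 50% | (20×3)^(1/2) = 7.7 | (10^3×10^4)^(1/2) = 3,162 | (75+50)/2 = 62.5% |
| 2+3+4 or 2+3+5 | 30 | 10/30 = 33% | (20×3×3)^(1/3) = 5.6 | (10^3×10^4×10^4)^(1/3) = 4,642 | (75+50+50)/3 = 58.3% |
| 2+3+4+5 | 40 | 10/40 = 25% | (20×3×3×3)^(1/4) = 4.8 | (10^3×10^4×10^4×10^4)^(1/4) = 5,623 | (75+50+50+50)/4 = 56.3% |

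GMFR thus appears 2.6 to 4.1 times higher at the low dose, while GMT appears 3.2 to 5.6 times higher at the high dose. The adverse event rate appears 12.5 to 18.8 points lower at the high dose.

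**Other assumed values, over the same readings.**

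- GMT: if the seropositive GMT is 2 to 8 times the seronegative, the spurious high/low ratio is 2^0.5 = 1.41 to 8^0.75 = 4.76.
- Adverse events: for p from 20% to 70%, the spurious gap is 0.5×0.2×0.8 = 8 points to 0.75×0.5×0.5 = 19 points.
- True ordering reversed: with GMFRs of 16 and 2 at the low dose and a true doubling at the high dose (32 and 4), the table shows 6.7 to 11.3 against 16. With p = 40% low and 50% high, it shows 56% to 62.5% against 64%.
- True ordering kept: with GMFRs of 8 and 4 and a true doubling, it shows 9.5 to 11.3 against 8. The order is right, but the twofold effect is understated.

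**After the fix.** Cohort 1 versus Cohort 2 has the same serostatus, route and schedule. With no dose effect it shows equal results on every endpoint. With p = 40% and 50% it shows 1−0.6² = 64% versus 1−0.5² = 75%, the correct order.

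**The case against.** The strongest reply is that nothing valid is lost. The same sentence lists by-cohort summaries first, so Cohort 1 versus Cohort 2 will be tabulated for every endpoint. The analysis is descriptive, no selection rule or test uses the pooled table, and the safety review committee decides on enrolment cohort by cohort. This stands. A reader might infer that the plan will lead to the wrong dose being chosen. The documents do not support that: it would require someone to rely on the pooled column and ignore the cohort columns.

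A reader might also infer that the all-cohorts summary favours a dose. It cannot, because it contrasts no doses. For immunogenicity it only averages priming with boosting, which is hard to interpret.

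It can further be said that the primary safety objective speaks of two dose levels for subcutaneous use, so only injected cohorts would be pooled. That may be the intention, but the pooling sentence does not say so, and even the narrowest reading joins Cohort 2 to Cohort 3.

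Finally, the supplied text is at synopsis level, so a fuller statistical section could define the pools. The absence of a restriction is established only for the text available.

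**Conclusion.** The point holds in limited form and should be fixed. As planned, the only table labelled by dose is confounded with serostatus and number of doses on every reading of 1×10^11 VP, and with route on some. This is a fact of the design and needs no assumed outcomes.

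The size of the distortion, its direction, and whether a true ordering reverses all rest on assumed values and on which cohorts are pooled. If seronegative and seropositive participants responded alike, the immunogenicity distortion would vanish. The defect is a misleading additional table in a dose-finding study, not a missing comparison.

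The valid contrast is itself limited. Cohorts 1 and 2 have 10 participants each and were to be enrolled in sequence, so they are matched by design but not randomised.

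It also does not always hold that 5×10^10 VP is Cohort 1 alone. If the fallback dosing were used, the low-dose pool could become mixed too, and a single cohort could contain both doses.

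**What to change.** Replace the pooling clause in Statistical Methods as follows:

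- Make dose-level summaries only within the same serostatus, schedule and route. As planned, that is Cohort 1 versus Cohort 2.
- Classify participants by the dose actually received if the fallback dosing is used. The cohort table footnote and the Study Design text differ on which cohorts it covers and must be reconciled.
- Define dose level for Cohort 5 (two administrations) and Cohort 6 (split between nostrils).
- Summarise immunogenicity for Cohorts 3 to 6 separately by route, and do not pool it across serostatus.
- Report solicited adverse events per dose administered and by route.
- Limit all-cohort summaries to safety, such as overall SAE, MAAE and HIV infection counts.

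The cost is a change of wording, smaller groups in each summary and slightly more table programming. No new data are needed.

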Solicited systemic AEs to be assessed include chills, fever, nausea, vomiting, diarrhoea, headache, fatigue, and myalgia. Safety visits and telephone calls will occur at scheduled times until 6 months after the last vaccine dose, and will be used to collect unsolicited AEs occurring since the last study contact, as well as any solicited AEs continuing beyond the 7-day period after vaccination.

Immunogenicity analyses will be conducted by collecting serum, peripheral blood mononuclear cell (PBMC) and saliva samples from individual patients before and after vaccinations to test for humoral- and cell- mediated immune responses. Immunogenicity assessments will be conducted for up to 1 year after the last vaccine dose.

Enrolment (planned):

Up to 60 participants will be enrolled in this study.

Eligibility Criteria:

Inclusion Criteria:

1. Adults, age 18 – 50 years, inclusive, at time of first study vaccination.
2. SARS-CoV-2 antibody positive for cohorts 3, 4, 5, and 6 (by a locally approved serology assay)
3. Able to understand and provide a signed informed consent that fulfils the relevant Institutional Review Board (IRB) or Independent Ethics Committee (IEC) guidelines.
4. Agrees to the collection of biospecimens (e.g., nasopharyngeal [NP] swabs) and venous blood per protocol.
5. Ability to attend required study visits and return for adequate follow-up, as required by this protocol.
6. Body mass index(BMI) <30.00kg/m²
7. Temperature < 38°C on day of first study vaccination.
8. Good general health as shown by medical history, physical exam, and screening laboratory tests
9. Screen negative for Tuberculosis per local screening guidelines
10. Male participants should all be at low risk of HIV acquisition based on pre-specified, validated criteria i.e. answering YES to any of the following questions:
 - a. Are you sexually abstinent?
 - b. Are you in a mutually monogamous relationship with a known HIV-uninfected partner?
 - c. Have you had only one partner in the preceding 12 months who is believed to be HIV-uninfected and with whom condoms were used regularly?

Laboratory Inclusion Values/ Results:

11. Alanine aminotransferase (ALT) <1.1 times the upper limit of normal
12. Serum Creatinine <80 umol/L in females and <106 umol/L in males
13. Haemoglobin >12.0g/dL in females and >13.5g/dL in males
14. Platelets >150 x 10⁹/L in all participants

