15. No serological evidence of chronic infection with Hepatitis B (hepatitis B surface antigen (HepBSAg) negative by a locally approved assay) done during the screening period
16. No serological evidence of chronic infection with Hepatitis C (hepatitis C antibody(anti-HCV) negative by a locally approved assay) done during the screening period
17. Negative for SARS-CoV-2 (PCR test) on NP swab(or other appropriate respiratory specimen) within 3 days (calendar days) prior to the first study vaccination

18. A negative serum or urine pregnancy test during screening and on the day of and prior to each dose must be documented before the vaccine is administered to a female participant of childbearing potential.
19. Negative for HIV-1 and -2 on blood test (by either 2 rapid tests or an ELISA, both must be locally approved assays) done during the screening period.

Reproductive Status:

20. Female participants of childbearing potential must agree to consistently practice effective contraception for sexual activity that may lead to pregnancy while on study and until at least 30 days after the last dose of the study vaccine. Effective contraception for female participants includes:

21. Intrauterine device (IUD), or
22. Hormonal contraception (oral/ injectable/ implant/ transdermal etc.)

Or;

23. Non-sterile male participants must agree to use a condom or spermicide while on study until at least 30 days after the last dose of the study vaccine.

Or;

24. Participant must not be of reproductive potential or sterile (as verified by medical records), such as:

- Having been diagnosed with menopause (with no menses for 1 year)
- Having undergone hysterectomy, bilateral oophorectomy or orchidectomy
- Having undergone surgical sterilization (e.g., vasectomy, tubal ligation)

[figure not shown]
Exclusion Criteria:

1. Serious adverse reaction to any vaccine, any unrelated medication or any component of the investigational vaccine, including a history of anaphylaxis and symptoms of a severe allergic reaction and history of allergies in the past.
2. Pregnant or breastfeeding women.
3. Live in a nursing home or long-term care facility.
4. Chronic lung disease or moderate to severe asthma
5. Bone marrow or organ transplant recipient
6. Diabetes.
7. Chronic kidney disease requiring dialysis.
8. Liver disease.
9. Any disease associated with acute fever, or any infection.
10. Chronic hepatitis B or hepatitis C infection.

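### In Cohorts 1-2, a SARS-CoV-2 infection during follow-up enters the primary antibody summaries as vaccine immunogenicity, although scheduled swabs and COVID-19 history could flag it

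*Combined protocol and SAP*

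**What the plan says.** **Primary immunogenicity.** The endpoint table lists "Percentage of participants who seroconverted (defined as 4-fold change in antibody titer relative to baseline", GMT and GMFR for S, RBD and N antibodies, and the same three measures for neutralising antibody. The Statistical Methods repeat the definition, "The percentage of participants who seroconverted (as defined as 4-fold change in antibody titer relative to baseline", add a Clopper-Pearson interval, and obtain GMT and GMFR by exponentiating log means. All endpoints are presented by cohort, by dose level and overall.

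**Who is measured.** Under Study Design, "Cohort 1-2 enrolled participants who were SARS-CoV-2 antibody serology negative". The reference therapy entry is marked not applicable. The vaccine is described as "encoding the SARS-CoV-2 S and N proteins".

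**What is collected (Table 9, Cohorts 1 & 2).**

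| Item | Visits after dose 1 |
|---|---|
| Immunogenicity samples | Days 8, 22, 29, 52; then 90, 180 and 365 days after dose 2 |
| PCR swabs | Days 8, 22, 29, 52; then 90, 180, 270 and 365 days after dose 2 |
| COVID-19 history | Every visit and call to 180 days after dose 2, and at 365 days |

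**Safety.** One primary endpoint is "Incidence and severity of solicited systemic reactogenicity AEs through 1 week post final vaccine administration"; solicited events are "collected using diary cards for 7 days following any dose of vaccine". Table 9 also schedules a baseline reactogenicity assessment at both dosing visits. Its footnote j says this covers signs or symptoms that could be confused with reactogenicity.

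**Use of PCR.** In the text available, PCR results serve as an entry criterion (Inclusion 17) and otherwise appear only as a schedule row. The Statistical Methods use neither the swabs nor the COVID-19 history.

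**The concern.** A first infection in a seronegative person can itself produce a 4-fold rise and raise S, RBD, N and neutralising titers. Under the stated definitions that person counts as a responder, and the titers enter the cohort mean. Nothing else in the design exposes the problem. There is no unvaccinated group to show background infection, and the usual device of reading anti-N as a marker of infection fails because the vaccine encodes N.

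The synopsis says the study is to choose a dose for later trials, and Cohorts 1 and 2, with 10 participants each, are the only two-dose comparison of the two subcutaneous levels. Cohort 2 opens only after the Day 8 safety review of Cohort 1, so the cohorts run at different calendar times and may meet different infection pressure. A difference in infections could then resemble a difference between doses. The reported intervals would not show this, because it is a bias and not sampling error.

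**Working it through.** The plan states no power, precision or infection figure, so there is none to reproduce. The documents supply n = 10 per cohort, the 4-fold definition, the Clopper-Pearson method and the visit schedule. Infection rates, fold rises and the 70% vaccine response are assumed for illustration.

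**1. Chance of at least one infection in a cohort of 10.** With weekly rate r, the risk per participant from Day 1 to Day 52 (51 days) is q = 1 - (1 - r)^(51/7). The chance for a cohort is 1 - (1 - q)^10.

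| r per week | q | At least one in 10 |
|---|---|---|
| 0.25% | 1.8% | 17% |
| 0.5% | 3.6% | 31% |
| 1% | 7.1% | 52% |
| 2% | 13.7% | 77% |

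Over the whole follow-up, assumed cumulative risks of 2%, 5%, 10%, 20% and 30% give 18%, 40%, 65%, 89% and 97%. Late samples are therefore the most exposed.

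**2. Effect on the 4-fold response, worst case.** Suppose 7 of 10 respond to vaccine and the infected participant is one of the other three.

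- Vaccine response alone: 7/10 = 70% (34.8-93.3%, a width of 58.5 points).
- As the plan counts it: 8/10 = 80% (44.4-97.5%).
- With that participant set aside: 7/9 = 77.8% (40.0-97.2%).

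**3. Effect on the 4-fold response, on average.** Suppose one infection strikes at random, independently of vaccine response. It hits a non-responder with probability 0.3.

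- As the plan counts it: 0.3 × 80% + 0.7 × 70% = 73%.
- With the infected participant set aside: 0.3 × 7/9 + 0.7 × 6/9 = 70%.

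So setting aside is unbiased if infection is independent of response, but not otherwise. More generally the plan's summary is too high by (1 - 0.7) × q. For the four rates above, Day 1 to Day 52, that is 0.5, 1.1, 2.1 and 4.1 points. These are upper figures, because they assume every infection yields a 4-fold rise by Day 52.

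**4. Effect on GMFR.** One participant of 10 with an extra F-fold rise multiplies the cohort GMFR by F^(1/10). For F = 4, 16 and 64 this is 1.15, 1.32 and 1.52.

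**5. What the swabs can miss.** From Day 29 to Day 52 the gap is 23 days (17 to 29 with the visit windows), bridged only by COVID-19 history at the Day 36 and Day 43 calls. Later gaps are 90 - 30 = 60, 180 - 90 = 90, 270 - 180 = 90 and 365 - 270 = 95 days. A symptomless infection inside a gap may go unflagged.

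**The case against.** **The plan never calls these results vaccine effects.** A reader might infer that it attributes COVID-19 symptoms to the vaccine, and that such events should be removed from the safety tables. The documents do not support this. Reporting treatment-emergent events whatever their cause is normal, and the Day 22 baseline assessment records overlapping symptoms already present at dose 2. It does not cover onset during the diary week, but a footnote or listing is enough for that. The immunogenicity part stands: titers and 4-fold rises are primary measures of response to the vaccine, and nothing separates the infected.

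**The effect is small.** This is correct. Even the worst case of 10 points per infection is far inside an interval 58.5 points wide, and the average shift is smaller. The plan has no hypothesis test and no numerical dose-selection rule, so no decision is shown to change.

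**Setting samples aside corrects little and can bias.** In the worst case it removes only 2.2 of the 10 points (80% to 77.8%). It also conditions on an event after vaccination. If poor responders are infected more often, the remaining participants look better than the cohort would have. This stands, and it is why the second summary can only be a sensitivity analysis.

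**The absence rests on a synopsis and schedule.** This also stands. Footnote d points to a Table 12 that is not in the available text, and no analysis sets are defined there at all. A rule may exist elsewhere.

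**Conclusion.** The point holds for immunogenicity in Cohorts 1-2. As written, an on-study infection is reported as vaccine response at any sample up to 365 days after dose 2, although the data to flag it are scheduled. The size is modest: at most 10 percentage points per infection per cohort of 10, or a GMFR multiplied by 1.15 to 1.52 under assumed 4- to 64-fold rises. How often it happens depends on infection rates that the documents do not give. This is a cheap improvement, conditional on no rule existing in text outside the synopsis and Table 9.

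Two further inferences are not supported:

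- **Safety Review Committee gates.** A reader might conclude that they are untouched because they close at Day 8. That does not follow: the entry PCR need only be "within 3 days (calendar days) prior to the first study vaccination", so an infection incubating at entry could cause symptoms in the first week. Nor do the documents show that any gate was affected.
- **Dose 2.** Inclusion 7 reads "Temperature < 38°C on day of first study vaccination", and the PCR criterion is likewise tied to the first vaccination, whereas the pregnancy test is required before each dose. A reader might see a major dosing gap. It is secondary: Cohorts 1-2 are described as already enrolled, so it applies only if second doses remain.

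**What to change.** 1. Keep the all-dosed summaries as primary.
2. Add one sensitivity summary of GMT, GMFR and 4-fold response for Cohorts 1-2, at every immunogenicity visit through 365 days after dose 2. For each participant with a positive PCR or recorded COVID-19, set aside samples taken after the last negative swab before that first evidence. For example, a participant negative on Day 22 and positive on Day 29 loses the samples from Day 29 onward. One negative at 90 days and positive at 180 days after dose 2 loses the 180- and 365-day samples.
3. Report the number flagged per cohort and visit, including zero.
4. For safety, exclude nothing. List or footnote solicited and unsolicited events that coincide with a positive PCR or recorded COVID-19.
5. Only if second doses remain, apply the fever and PCR conditions before each vaccination. This would not prevent a later infection-driven rise.
6. If a rule already exists elsewhere, a cross-reference to it in the Statistical Methods is enough.

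**Cost.** One flag, one repeat of planned tables and one listing, with no new visit or sample. The sensitivity summary will have fewer than 10 per cohort wherever anyone is flagged, will miss some infections between swabs, and may carry selection if infection depends on vaccine response. State these limits beside it.
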